6. Study Duration and Visits: The study duration was (3 months) and was comprised of a total of 4 visits: Screening and hygienic phase therapy (weeks -2 to -1), Baseline (Visit 1, Day 0), Visit 2 (14 days), Visit 3 (45 days), Visit 4 (90 days).
7. Subjects received an Oral Hygiene Kit at Visit 1. The Modified Gingival Index (MGI), Bleeding on Probing (BOP) and Plaque Index (PI), Pocket depth and radiographs were measured, and all oral tissues examined (baseline examination). Subjects returned for Visit 2 in 14 days \pm 3 days to: 1) assess and record changes in indices and oral health and any adverse conditions. Visit 3 (45 days \pm 7) was a compliance visit for study drug utilization. Visit 4 (90 days \pm 7) was a repeat of Visit 1. Samples for microbiome analysis were collected at baseline (Visit 1), Day 14 (Visit 2), and Day 90 (Visit 4).
8. All parameters for clinical exam were calibrated between the examiners involved with the study.

[6] Study Materials (Oral Hygiene Kit)

STUDY DRUG

Both the active and placebo drugs were provided in liquid form, intended for oral administration. Sample products were labeled by the manufacturer and shipped directly to the site.

ADMINISTRATION

After tooth brushing in the morning and evening, the study product was administered orally using a cup that measures 15 mL of oral rinse, swishing in the oral cavity for 30 seconds and expectorating.

[7] Subjects

Subject recruitment occurred at the discretion of the Principal Investigator. After being recruited, potential subjects were informed of the purpose of the study and guided through HIPAA documentation and the informed consent process. Upon their understanding of the study, HIPAA regulations, and their agreement with the terms of the informed consent, subjects indicated so by signing the forms. The eligibility of potential subjects was determined through a series of screening interviews and an oral examination. Following screening, those potential subjects who retained eligibility were enrolled in the study at the discretion of the Principal Investigator. Approximately 75 subjects were screened to provide 54 enrollees. Once these subjects were randomized, study enrollment was complete.

Number of subjects: 54 subjects

Age: 18 years to 80 years

Gender: Both male and female subjects entered this study.

Remaining Natural Teeth: Minimum of 20

[8] Subject Eligibility Criteria

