- a) Gingival inflammation (MGI)

Secondary analyses were the comparison of data with respect to product effectiveness:

- a) Reduction in bleeding on probing (BOP) and Turesky modification of the Quigley-Hein Plaque Index (PI) grading on all natural teeth in the dentition

The primary statistical analytic framework was the repeated measures analysis of variance on three primary outcomes: probing depth, gingival index, and plaque. The primary hypothesis tested was the treatment by time interaction, i.e., did one treatment work better during the observations of these three outcomes? In other words, not just the total change, but also the rate of that change might differ between treatments. The proposed analysis was based on data that were generally normally distributed and similarly. If not, data transformations or link functions were used.

Outcomes

Raw data were collected from examinations of each tooth with regard to probing depth, gingival index, and plaque. Data were collected over three time periods, recorded into patient files, and transferred to Excel Workbooks, with one Workbook per patient. Each Workbook contained three tabs, one for each visit.

The raw data were combined as two levels of indexes for the three measures. The first outcome was a global score index of probing depth, gingival index, and plaque measurement. The global index was derived from individual tooth scores for each measure divided by the number of teeth measured. The second index derived from the same raw data described the three measures in terms of average scores for implant and non-implant teeth.

For the second analysis, implanted tooth data were separated from normal teeth data within each patient. Implant scores for each patient were averaged for probing depth, gingival index, and plaque scores. If a patient had one implant, each score was identical to the single measurement. With more than one implant, a single implant score for each patient was derived from averaging each of the three measures over the three observation periods. Likewise for each patient, the non-implanted teeth measures were averaged for each of the three times of assessment.

Individual patient data of the averages of the implant and non-implant teeth were calculated for each time period and transferred to a master data sheet.

Data Management and Statistical Analysis

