The patients' data on the three measures were recorded within the Excel Workbooks under three tabs representing the first, second, and third clinical observation periods. So each tab recorded three measures. The first and last tabs recorded probing depth, gingival index, and plaque. The second visit included only gingival index and plaque. Each patient had an individual Excel Workbook. Data were sorted into analysis format through two Excel macros that created a single master data for global scores and a single one for implant and non-implant scores. Data files were saved in comma separated value (csv) format in both wide and long formats for R and SPSS data management, inspection, cleaning, and analyses.

Since many individual variable distributions varied substantially from normal, a gamma log-link function was applied to reduce bias in most statistical tests.

Label Key and Lot #s for Peri-Implant Mucositis Study with Stony Brook University

Rowpar Pharmaceuticals, Inc., released the test material label codes after completion of the clinical study and statistical analysis of the data. The products were labelled as follows:

Study Number: SBU-RPR-Peri-Implant Mucositis-2018

Oral Rinse A: ClōSYS Placebo Oral Rinse, Lot #: 2-80516

Oral Rinse X: ClōSYS® Ultra Sensitive (Unflavored) Oral Rinse, Lot #: 8122A 14-80430

Results

Patients

Fifty-two percent (29/56) of patients in both groups had only one implant. Patients in the control group (Group A) had a total of 47 implants: 11 patients had just one implant, 13 had 2, 2 had 3, and 1 had 4 implants. In the test group (Group X), there were 42 total implants in 26 patients: 18 had 1 implant, 9 had 2, and 2 had 3 implants (see Figure 1). Table 1 gives average values (and standard error of the mean) of Gingivitis Index, Plaque score, and Probing depth at baseline.

Figure 1. Bar chart of numbers of implants per person in control group (Group A) and test group (Group X).

[figure not shown]

Table 1. Patient dental measures at baseline.

		n of patients	n of implants	Modified Gingivitis Index (MGI) (sem)	Plaque score (PS) (sem)	Probing Depth mean (sem)
Control Group (Group A)	implants	27	47	2.06 (0.048)	2.77 (0.115)	3.40 (0.109)

	non-implanted teeth			1.87 (0.039)	2.32 (0.101)	2.72 (0.099)
Test Group (Group X)	implants	26	39	2.82 (0.049)	2.84 (0.057)	2.447 (0.080)
	non-implanted teeth			2.01 (0.028)	2.99 (0.078)	2.65 (0.079)

Global Score Analyses

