Slope of probing depth, time 1 to 3	57	-1.47	0.015	-0.10632	0.323886
Slope of gingivitis index, time 1 to 3	57	-0.99	-0.03	-0.24351	0.221807
Slope of plaque score, time 1 to 3	57	-1.53	-0.045	-0.45254	0.358255
Valid N (listwise)	57				

Global Probing Depths (GPD)

Global probing depth (GPD) collected at the first visit did not differ significantly between groups; control group's (Group A) initial GPD was 2.76 (SEM = 0.092) interval, and 2.68 (0.071) for test group (Group X), a non-significant statistical difference ($p = 0.48$).

Neither did the GPD score differ between final visits of control group (Group A) (GPD = 2.64 (0.130) and test group (Group X) (GPDI = 2.37, (0.166), $t = 1.27$, $df = 55$, $p = 0.28$. Nonetheless, the GPD decreased significantly for control group (Group A), ($p = 0.028$; for X, $p < 0.001$) for both groups, but the group decreases were not significantly different from each other. Both mouthwashes reduced probing depth similarly.

The key signal of treatment effectiveness is a statistically significant treatment-by-time interaction, where improvement over time is greater for one treatment than another. Nearly parallel lines in Figure 2 and statistical testing indicated no appreciable and significant treatment-by-time interaction for GPD (See Figure 2, Figure 3).

Figure 2. Interaction plot showing that group assignment did not interact with time for probing depth.

[figure not shown]

Figure 3. Boxplots of probing depth results from treatment by control group (Group A) and test group (Group X). Probing depth was not affected differentially by the mouthwash treatments. Both conditions reduced probing depth slightly but not statistically significant.

Global Plaque Score

Control group (Group A) and test group (Group X) differed significantly in global plaque score (GPS) at initial assessment, requiring an additional analysis of covariance to confirm that a significant time by treatment interaction was not an artifact from the initial difference in GPS (See interaction plot, Figure 4, detailed in Figure 5). The test group's (Group X) initial average GPS was 3.00 (SEM = 0.071) versus 2.35 (0.097) for the control group (Group A), a significant difference ($t = -5.45$, $df = 50$, $p < 0.001$). At assessment 3, the last observation, the test group's (Group X) GPS (1.57, SEM = 0.110) was significantly lower than that for the control group (Group A); GPS = 1.98 (0.110), $t = 2.633$, $df = 55$, $p = 0.011$.

[figure not shown]

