The gingivitis index is based on the Gingival Index system,² in this case, the global gingival index is GGI. The GGI was also significantly higher for the test group (Group X) at the initial visit; for the test group (Group X) = 2.03 (0.025) and GGI for the control group (Group A) = 1.91 (0.035), ($t = -2.89$, $df = 55$, $p = 0.006$). Figure 6 illustrates a potential interaction between treatment and time of observation that required statistical consideration and control. Again, GGI for visit 1 was used as a covariate so as not to over-estimate treatment effects on GGI represented in a time-by-treatment interaction. The ANCOVA upheld a statistically significant ($t = 2.12$, $df = 51$, $p = 0.039$) between treatments. Boxplots of the GGI across visits is shown in Figure 7. The test group (Group X) reduction in GGI was 27.3% versus the control group's (Group A) reduction of 20.4%, also statistically significant difference by repeated measures analysis of variance ($F = 8.141$, $df = 1$, $p = 0.0046$).

[figure not shown]

Figure 6. Interaction plot showing group assignment interacting with time on gingival index measures (GGI).

[figure not shown]

Figure 7. Boxplots of gingival index measures comparing treatment control group (Group A) and test group (Group X). Test group (Group X) started with higher gingival index levels. Gingival index decreased more and faster in test group (Group X) than in the control group (Group A), though both decreased significantly.

Differential Effects of Mouthwashes on Implants in Control Group (Group A) and Test Group (Group X)

Of particular interest was the specific effect that control mouthwash (rinse A) and test mouthwash (rinse X) might have on implant and non-implant sites across the three outcomes. Table 4 illustrates the overall study results of treatments and implants on the three outcomes. Probing depth was not different between treatments for implant and non-implant sites. Plaque and gingival indexes were improved significantly under test rinse Treatment (rinse X), with details described in Tables 5, 6, and 7 below. In addition, implant sites improved at a faster rate under test rinse Treatment (rinse X) conditions for both gingivitis and plaque.

Table 4. Omnibus test for main effects and interactions of control mouthwash (rinse A) and test mouthwash (rinse X) on implant and non-implant sites.

Sites of Implants responding differently to treatment					
All outcomes: measures in table					

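### Baseline means from the global file and the implant/non-implant file do not reconcile: test-arm whole-mouth probing depth (2.68) lies above both of its Table 1 components (2.65 and 2.447), and the two files cover different patients without explanation

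*Combined protocol and SAP*

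**What the plan says.** Section [11], Outcomes, defines the whole-mouth score: "The global index was derived from individual tooth scores for each measure divided by the number of teeth measured". It then says of the site-specific scores: "The second index derived from the same raw data described the three measures in terms of average scores for implant and non-implant teeth". Both summaries therefore come from one set of tooth-level records. Under Data Management and Statistical Analysis, "Data were sorted into analysis format through two Excel macros that created a single master data for global scores", with a separate single file for implant and non-implant scores.

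The component means are in "Table 1. Patient dental measures at baseline", for 27 control and 26 test patients with 47 and 39 implants. The whole-mouth means are in the results text. For probing depth the control group's "initial GPD was 2.76 (SEM = 0.092) interval, and 2.68 (0.071) for test group (Group X"); for the gingival index, "GGI for the control group (Group A) = 1.91 (0.035"). The whole-mouth analyses use 57 patients (Table 3; error df 55 in Table 2). The implant analyses use 53 (error df 102 = 2 x 53 - 4 in Tables 5-7). Section [7] sets "Remaining Natural Teeth: Minimum of 20", which limits the weight implants can carry in a whole-mouth mean.

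**The concern.** If both files summarise the same records, each patient's global score is a weighted mean of that patient's tooth and implant averages. Apart from any link between implant count and the implant-tooth difference, the arm mean must fall between the two component means and close to the tooth mean. One arm-by-measure cell breaks this outright and another fits only with an implausible weight.

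Tables 2 and 3 rest on one file; Tables 1 and 5-7 rest on the other. The Conclusions claim a preferential benefit at implant sites, and that claim depends on the implant file. Implants carry only about 6% of a whole-mouth mean. A whole-mouth discrepancy of 0.01 mm would therefore be 0.01/0.06 = 0.17 mm at the implants, if that is where it arose. Small gaps in the global means are worth tracing for that reason.

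**Working it through.** **1. Feasible implant weight.** Mean implants per patient are 47/27 = 1.74 (control) and 39/26 = 1.50 (test). With the minimum of 20 teeth the weight is at most 1.74/21.74 = 0.080 and 1.50/21.50 = 0.070. Assuming at most 32 positions in all, it is at least 1.74/32 = 0.054 and 1.50/32 = 0.047.

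**2. Implied weight,** w = (global - teeth)/(implants - teeth). Ranges allow for rounding of the printed means.

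| Arm, measure | Teeth | Implants | Global | w (range) | Reading |
|---|---|---|---|---|---|
| Control plaque | 2.32 | 2.77 | 2.35 | 0.067 (0.044 to 0.089) | reconciles |
| Control probing depth | 2.72 | 3.40 | 2.76 | 0.059 (0.044 to 0.074) | reconciles |
| Control MGI | 1.87 | 2.06 | 1.91 | 0.211 (0.158 to 0.263) | too high |
| Test plaque | 2.99 | 2.84 | 3.00 | -0.067 (-0.143 to 0) | at the rounding limit |
| Test MGI | 2.01 | 2.82 | 2.03 | 0.025 (0.012 to 0.037) | low |
| Test probing depth | 2.65 | 2.447 | 2.68 | -0.148 (-0.203 to -0.096) | impossible for one patient set |

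**3. Correlation between weight and implant-tooth difference, test probing depth.** I took 15, 9 and 2 patients with 1, 2 and 3 implants, 20 teeth each, and the most extreme correlation. The whole-mouth mean then rises about 0.008 mm above the tooth mean; 0.02-0.04 mm is needed.

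**4. Different patients.** The arm split of the 57 is not printed. Weighting the printed arm means to match Table 3 gives 28 control and 29 test; splits of 27/30 and 29/28 miss baseline plaque by 0.013 and 0.010. The Patients text agrees for the test arm: 18 + 9 + 2 = 29 patients and 42 implants, against 26 and 39 in Table 1. So three test patients and one control appear to be missing from the implant file.

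Mean baseline depth needed in the three test patients, with every rounding taken favourably:
- Table 1 at most: 2.655 - 0.047 x (2.655 - 2.4475) = 2.645.
- Needed: (29 x 2.675 - 26 x 2.645)/3 = 2.93 mm.
- With the extreme correlation of step 3, Table 1 allows 2.655 + 0.008 = 2.663, and the need falls to (77.575 - 69.238)/3 = 2.78 mm.

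**5. Can they average that much?** Table 3 shows a Day 90 probing-depth minimum of 0.
- Test, 2.37 (SEM 0.166), n = 29: total SS = 28 x 29 x 0.166² = 22.4. Three zeros use 18.8 and leave a residual SD of 0.378 (baseline SD 0.071 x √29 = 0.382). Four would need 26.1, which is impossible.
- Control, 2.64 (SEM 0.130), n = 28: total SS = 12.8. One zero uses 7.2 and leaves SD 0.46 (baseline 0.49). Two would need 15.0, which is impossible.

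Three test zeros and one control zero match 29 - 26 and 28 - 27. The slope is (time 3 - time 1)/2, since (2.50351 - 2.71614)/2 = -0.10632 as printed. A patient with baseline b and a Day 90 zero has slope -b/2. Table 2's total slope SS of 6.519 then requires the four b² to sum to at most 4 x 6.519 = 26.08. With the control b at least 2.04 (Table 3 minimum), the three test baselines average at most √((26.08 - 4.16)/3) = 2.70 mm. The other 26 must then average at least (77.575 - 8.10)/26 = 2.672 mm, against 2.645 (or 2.663) from Table 1.

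**6. Control MGI.** Favourable rounding gives 28 x 1.905 - 27 x (1.875 + 0.079 x 0.19) = 2.31 for the one extra control patient; Table 3's maximum is 2.23.

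**7. Is 2.447 a misprint?** (3.40 - 2.447)/√(0.109² + 0.080²) = 7.05, against the printed t = 7.07. Pooling the arms, (27 x 3.40 + 26 x 2.447)/53 = 2.93 with SEM 0.094, and teeth give 2.69 with SEM 0.063. These are the figures printed under Implants and Probing depth, where they are attributed to the control group. So 2.447 is the value in the analysed implant file.

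**The case against.** The strongest reply is that the two outputs do not describe the same patients. Three extra test patients averaging about 2.93 mm or more would close the probing-depth gap, and Table 3's baseline range is 2.04-4.63. The counter in step 5 is inferential: it needs the 28/29 split, the four zeros, and the omitted patients being those with zeros. No passage states any of these. Without the control zero the cap is √(26.08/3) = 2.95 mm, just above the need. This stands as a limit on certainty. It does not restore agreement, because the zero counts are the largest the SEMs allow, leave residual SDs near baseline and match the missing patients in both arms.

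The MGI row is weaker still. An extreme correlation raises the control mean by 0.029 over the tooth mean, which with favourable rounding and the extra patient is enough. Outcomes also says that scores for patients with several implants were averaged over the three observation periods, although it later describes averages for each period. On the literal reading, 16 of 27 control patients are affected. Assume the printed 19% fall in control-implant MGI (the same paragraph also prints 57%), linear across visits. The true baseline is then 2.06 x 27/(11 + 16 x 0.905) = 2.18, and the extra patient needs only about 2.06. That reading does not help test probing depth, where the text reports a slight rise at implants.

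Test MGI and test plaque can be met by three extra patients averaging about 1.78 and 3.16, inside Table 3's ranges.

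A reader might go further and infer that a macro malfunctioned, or that 2.447 is wrong. The documents support neither. They report no macro fault, and 2.447 agrees with the t statistic and the pooled mean and SEM. That agreement shows what the file contains, not that the file is right, but it identifies no particular cell as the error.

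**Conclusion.** Wrong as written, with the cause open. On a single patient set, test-arm baseline probing depth is contradictory: 2.68 cannot come from 2.65 and 2.447. On the differing sets the contradiction probably remains. The three omitted test patients need about 2.93 mm (2.78 mm at the extreme correlation) against a cap of about 2.70 mm, a shortfall of 0.027 mm (0.009 mm) in the mean of the other 26. This rests on the inferred split and on identifying the omitted patients with the Day 90 zeros. Control MGI is a second warning sign that could have an innocent explanation. Two of the six rows reconcile, so the finding is not that the global means as a whole cannot be rebuilt. The unexplained drop from 57 to 53 patients needs an answer whatever the cause.

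**What to change.** Rebuild both master files from the patient workbooks on one stated patient set.

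- Account for the four patients absent from the implant file, and say whether the Day 90 zeros are measurements or missing visits entered as zero.
- For every patient, visit and measure, check that global x sites = tooth mean x teeth + implant mean x implants. List and correct each failure.
- State whether scores for patients with several implants are averaged within each visit or across visits.
- Correct the control-group label on the pooled 2.93 and 2.69.
- Reissue Tables 1-7 and the implant text, and treat implant-level conclusions as provisional until the check passes.

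No replacement for 2.447 should be entered except from the workbooks. The cost is a short script and a re-run of existing analyses, with no new data or patients. Some implant figures may become less favourable.

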From raw data of individual teeth, each patient received a global index of periodontal disease, gingival index, and plaque for each visit. The global index for each of these measurements was found by dividing the sums of patient probing depth, gingival index, and plaque findings collected for each tooth by the number of teeth assessed. Over the three assessment periods, global scores of probing depth, gingival index, and plaque were collected for the first and last visits with probing depth scores not collected during the second visit. These outcomes are measured as individual slopes of responses across the three observation visits. The slope represents the rate of change.

The overall view of the response of each measure to the treatment group is summarized in the following general linear model Table 2. Table 3 shows the cell statistics for the slopes of each condition and outcomes reported in Table 2.

Table 2. Master table of variance components attributable to treatment on individual rates of change on the three measures: probing depth, gingival index, and plaque.

Source	Variable	Type III SS	df	MS	F	Sig.
Group	Slope of probing depth, time 1 to 3	0.125	1	0.125	1.191	0.28
	Slope of gingivitis index, time 1 to 3	0.485	1	0.485	11.748	0.001
	Slope of plaque score, time 1 to 3	4.019	1	4.019	69.751	0.000
Error	Slope of probing depth, time 1 to 3	5.75	55	0.105		
	Slope of gingivitis index, time 1 to 3	2.27	55	0.041		
	Slope of plaque score, time 1 to 3	3.169	55	0.058		
Total	Slope of probing depth, time 1 to 3	6.519	57			

Slope of gingivitis index, time 1 to 3	6.135	57
Slope of plaque score, time 1 to 3	18.861	57
Corrected Total	Slope of probing depth, time 1 to 3	5.875
	Slope of gingivitis index, time 1 to 3	2.755
	Slope of plaque score, time 1 to 3	7.187
	R Squared = .021 (Adjusted R Squared = .003)	
	R Squared = .176 (Adjusted R Squared = .161)	
	R Squared = .559 (Adjusted R Squared = .551)	

Table 3. Details of cell statistics for analysis described in Table 2.

Descriptive Statistics					
	N	Minimum	Maximum	Mean	Std. Deviation
Probing depth at time 1	57	2.04	4.63	2.71614	0.432843
Probing depth at time 3	57	0	4.42	2.50351	0.804056
Gingivitis index at time 1	57	1.41	2.23	1.97158	0.172065
Gingivitis index at time 2	57	0	2	1.71754	0.364095
Gingivitis index at time 3	57	0	1.92	1.48456	0.451688
Plaque score at time 1	57	1.47	3.54	2.67895	0.555475
Plaque score at time 2	57	0	3.11	2.19614	0.596444
Plaque score at time 3	57	0	2.92	1.77386	0.618124

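### The text reports a gamma log link for most tests, yet every printed model table is a Gaussian linear model, and the Table 2 slopes and zero follow-up scores cannot be gamma responses

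*Combined protocol and SAP*

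**What the plan says.** All places are in the combined protocol and SAP, section [11].

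- **Statistical Evaluation.** "The primary statistical analytic framework was the repeated measures analysis of variance on three primary outcomes". Approximate normality is assumed, with a fallback: "If not, data transformations or link functions were used".
- **Data Management and Statistical Analysis.** Many variables are reported as far from normal, and so "a gamma log-link function was applied to reduce bias in most statistical tests".
- **Global Score Analyses.** "These outcomes are measured as individual slopes of responses across the three observation visits". The comparison of arms is then "summarized in the following general linear model Table 2". Beneath that table, the line for the gingival index reads "R Squared = .176 (Adjusted R Squared = .161".
- **Tables 4 to 7.** All are Type III sum-of-squares tables with mean squares and F ratios. The captions of Tables 5 and 6 also name a general linear model.

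No result is labelled as a gamma model. No ratio of means, log-scale coefficient, deviance or Wald statistic is printed, and no rule for zero scores is given.

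**The concern.** The text says that the normality condition failed and that the fallback was used for most tests. A reader would take it that most p-values come from a model suited to skewed, positive data. A gamma model needs strictly positive responses. The slopes are mostly negative and the follow-up scores include zeros, while the printed tables are in least-squares form. If so, the tests on view are the normal-theory tests that the fallback was meant to replace, applied to data with a few extreme values. MGI, the outcome named for the primary objective, carries p = 0.001 (Table 2), 0.039 (ANCOVA) and 0.0046 (repeated measures). The reader cannot tell which model, or which patients, lie behind each.

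**Working it through.** **1. Could the responses be gamma?** Ranges from Table 3 (n = 57):

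- MGI slope: -0.99 to -0.03
- Plaque slope: -1.53 to -0.045
- Probing-depth slope: -1.47 to +0.015
- Minimum 0 for MGI and plaque at times 2 and 3, and for probing depth at time 3
- Baseline minima 2.04 (probing depth), 1.41 (MGI) and 1.47 (plaque)

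The gamma likelihood is defined only above 0, and R's glm stops with an error on any non-positive gamma response. The slopes are ruled out, and so are the follow-up global scores unless the zeros were dropped or altered. Baseline scores could be gamma.

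**2. Reproducing Table 2.** Formulas: F = SS(group) / [SS(error)/55]; R² = SS(group) / [SS(group) + SS(error)]; corrected total = 56 × SD², with the SD from Table 3.

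| Slope | F | printed | R² | printed | 56 × SD² | printed |
|---|---|---|---|---|---|---|
| Probing depth | 0.125/(5.75/55) = 1.196 | 1.191 | .021 | .021 | 56 × 0.323886² = 5.875 | 5.875 |
| MGI | 0.485/(2.27/55) = 11.751 | 11.748 | .176 | .176 | 56 × 0.221807² = 2.755 | 2.755 |
| Plaque | 4.019/(3.169/55) = 69.752 | 69.751 | .559 | .559 | 56 × 0.358255² = 7.187 | 7.187 |

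The mean slope is (time 3 - time 1)/2; for MGI, (1.48456 - 1.97158)/2 = -0.24351, as printed. Table 2 is therefore ordinary least squares on untransformed slopes of all 57 patients.

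**3. Tables 4 to 7.** F = MS/MSE holds within rounding. For example:

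- Table 4, three-way term: 16.127/(60.738/204) = 54.166 (printed 54.166)
- Table 5, time by group: 0.941/(2.737/102) = 35.07 (35.047)
- Table 6, implant by group: 8.613/(11.118/102) = 79.02 (79.021)
- Table 7, implant by group: 7.532/(49.62/102) = 15.483 (15.483)

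Error df of 102 = 2 × 53 - 4 and 204 = 4 × 53 - 8 point to 53 patients, as in Table 1. Taking 53 patients × 2 site types × 3 visits = 318 values, the intercepts return raw-scale means: √(1207.001/318) = 1.948 for Table 6 (gingival) and √(1596.963/318) = 2.241 for Table 7 (plaque). Table 4, with two measures (636 values), gives √(2790.339/636) = 2.095, the average of those two. Tables 4, 6 and 7 are thus on the untransformed scale. Table 5 prints no intercept, so its scale cannot be checked this way.

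**4. In-text tests.**

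- Final plaque: (1.98 - 1.57)/√(0.110² + 0.110²) = 2.64 (printed t = 2.633, df 55). This is an ordinary t-test.
- Plaque change: the printed t = 8.35 is √69.751 = 8.35, the Table 2 test again.
- MGI ANCOVA: t = 2.12, df 51. With 57 patients and three parameters (intercept, group, baseline) the error df would be 54; 51 would fit 54 patients. The model is not identifiable.
- MGI repeated measures: F = 8.141 with p = 0.0046 needs a denominator df of about 280 to 404, more than 57 × 3 = 171 patient-visits. The model is not identifiable.
- Bayesian analysis of plaque: no likelihood is stated.

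**5. How far the extremes matter in Table 2.** Share of the corrected total supplied by one patient at the minimum, (minimum - mean)²/corrected total:

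- Probing depth: (-1.47 + 0.10632)²/5.875 = 32%, at 4.2 SD below the mean
- MGI: (-0.99 + 0.24351)²/2.755 = 20%, at 3.4 SD
- Plaque: (-1.53 + 0.45254)²/7.187 = 16%, at 3.0 SD

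These minima would result from a final score of 0 after baselines of 2.94, 1.98 and 3.06 (twice the slope), all inside the printed baseline ranges.

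**6. How many zeros are possible.** With k zeros among 57, the sum of squares left for the other scores is 56 × SD² - k × m² - (57 - k) × [57m/(57 - k) - m]², which must not be negative. For MGI at time 3 it is 1.944 at k = 4 and -0.654 at k = 5, so there are at most 4 zeros. The other limits are 2 (MGI time 2), 3 (plaque time 2), 6 (plaque time 3) and 5 (probing depth time 3).

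**7. Would a log scale change anything?** A rough check from the printed final means and SEMs takes log(X/A), with SE = √[(SEM/mean)² in A + (SEM/mean)² in X].

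- Plaque: ratio 1.57/1.98 = 0.79 (95% CI 0.67 to 0.94), z = -2.59, against the printed t = 2.633
- Probing depth: ratio 2.37/2.64 = 0.90 (0.76 to 1.06), z = -1.26, against the printed t = 1.27

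Both are essentially unchanged. Final MGI means by arm are not printed, so MGI cannot be checked. This is not a gamma fit, and it uses the means as printed, whatever the zeros are.

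**The case against.** The text says most tests, not all, and it does not call the printed tables gamma: Tables 2, 5 and 6 are openly described as general linear models. The MGI ANCOVA has df 51, which would fit a gamma model that lost three non-positive scores, though other exclusions would fit equally well. The argument from negative slopes and zeros does not reach Tables 4 to 7, which analyse implant and non-implant scores in 53 patients with no minima printed; the zero-scored patients may be among those left out. Where the log-scale effect can be approximated, it is small.

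All of this stands, and it limits the point. A reader might infer that no reported result came from a gamma model, or that the reported p-values are wrong. The documents support neither: the MGI ANCOVA, the F = 8.141 test and the Bayesian analysis do not show their model, and no reversal can be demonstrated. Nor do the documents say that the zeros are missing visits.

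The contradiction remains. Tables 4 to 7 are shown to be Gaussian by their own sums of squares, not by the range of their data. Correct labels on three tables do not help a reader to find the tests that the gamma sentence describes.

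**Conclusion.** The point holds in this limited form. All five printed model tables are Gaussian linear models, contrary to what the statement about most tests leads a reader to expect. For Table 2 a gamma model is impossible, and for the follow-up global scores it is impossible without an undocumented handling of zeros. The printed tables therefore lack the protection against non-normality that the text claims, and in Table 2 a single patient can supply 16% to 32% of the variation.

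The effect on the conclusions is unknown: about nil for final plaque and probing depth on a rough log-scale check, and not computable for MGI. The raw-scale reading of Tables 4, 6 and 7 assumes 53 patients with complete visits. That some zeros are missing visits coded as 0 is an inference, resting mainly on the implausibility of a whole-mouth mean probing depth of 0.

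**What to change.** 1. Correct the methods text to say that Tables 2 and 4 to 7 are Gaussian linear models. Name each result, if any, that used the gamma log link, with its patients and error df; the MGI ANCOVA, the F = 8.141 test and the Bayesian analysis need this most.
2. Check the zero follow-up scores against the patient workbooks. State for each arm and visit whether they are real or missing visits, and how they were handled.
3. For the Table 2 slopes, print a permutation test or a test with robust standard errors beside the linear result.
4. For visit-level MGI and plaque, print a gamma log-link mixed model or GEE with group by visit on the valid positive scores, as a sensitivity analysis. If some zeros prove genuine, report how many the gamma model leaves out in each arm, since these are the best scores.

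The cost is one extra model per outcome, a check of existing records and corrected text. Some p-values may become less favourable.
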